6.1.4. Product Accountability

The investigator is responsible for pamiparib accountability, reconciliation, and record maintenance. In accordance with all applicable regulatory requirements, the investigator or designated study center personnel must maintain pamiparib drug accountability records throughout the course of the study. This person(s) will document the amount of pamiparib received from the sponsor, the amount supplied, and/or administered to and returned by patients, if applicable.

After completion of the study, all unused pamiparib will be inventoried and packaged for return shipment. The inventoried supplies will be returned to the sponsor or destroyed on site, after receiving written sponsor approval.

All unused TMZ will be destroyed on site according to regulations and local guidelines.

6.1.5. Assessment of Treatment Compliance

On all visits to the study center, patients will be questioned in regard to compliance with study instructions.

6.1.6. Treatment of Overdose from Study Drugs

Overdose is defined as a patient having taken (accidentally or intentionally) a dose of pamiparib or TMZ that exceeded the dose assigned per protocol by $\geq 20\%$. Patients with a suspected overdose should be managed with appropriate supportive therapy as determined by the investigator in consultation with the Medical Monitor. Any AEs occurring as a result of an overdose should be reported to the Medical Monitor as well as being included in standard AE reporting.

6.1.7. Occupational Safety

Pamiparib is not expected to pose significant occupational safety risks to the study center personnel under normal conditions of use and administration. A material safety data sheet describing occupational hazards and recommended handling precautions will be provided to the investigator, where this is required by local laws, or is available upon request from the sponsor.

6.2. Concomitant Medications and Non-Drug Therapies

6.2.1. Permitted Medications

All treatments and supportive care, including antiemetic therapy, hematopoietic growth factors and/or red blood cell/platelet transfusions, that the investigator considers necessary for a patient's welfare may be administered at the discretion of the investigator in keeping with the local standards of medical care. All concomitant medications taken during the study will be recorded on the electronic case report form (eCRF) including all prescription and over-the-counter (OTC) drugs, herbal supplements, and intravenous (IV) medications and fluids. If changes occur during the study period, documentation of changes in drug dosage, frequency, route, and date will also be included on the eCRF.

All concomitant medications taken by or administered to the patient within 28 days before Day 1 and 30 days after the last day of study drug should be recorded.

The eCRF entry must include the dose, regimen, route, indication, and start and stop dates of use of the prior and concomitant medications.

6.2.2. Prohibited Medications

Patients are not allowed to receive other anticancer therapy, including surgery, radiation therapy (RT), and cytotoxic, biologic, investigational agent, anticancer Chinese medicine, or hormone therapy. Bisphosphonate and denosumab use are permitted if the patient had already been receiving it at a stable dose ≥ 28 days prior to Day 1. Palliative treatment of isolated lesions (except target lesions) with local radiation therapy is allowed.

The primary metabolic pathway for pamiparib involves the CYP3A isoform, thus co-administration of strong/moderate inhibitors of CYP3A with pamiparib should be avoided. Also avoid strong CYP3A inducers with pamiparib. Please refer to the drugs/substances presented in [Appendix 4](#) and to <http://medicine.iupui.edu/clinpharm/ddis/main-table/> for a more complete list of medications that should be avoided.

Avoid the use of drugs that are known to cause prolongation in QT/QTc interval and/or induce Torsades des Pointes. Please refer to [Appendix 6](#) for a list of these drugs. If the use of any of these drugs is necessary, the Medical Monitor should be contacted.

Avoid valproic acid as it decreases oral clearance of temozolomide (see package insert for temozolomide).

Grapefruit juice is not allowed throughout the study. No other dietary restrictions will apply.

6.2.3. Medications to Be Used with Caution

Based on preliminary *in vitro* screening assays, pamiparib is not a strong inhibitor of other human CYP isoenzymes tested. It is a moderate inhibitor of CYP2C9 ($IC_{50} = 6.48 \mu M$). Investigators need to be aware that pamiparib has the potential to interfere with the appropriate metabolism of medications that rely on CYP2C9 and follow the prescribing information recommendations for use with CYP2C9 inhibitors. Therefore, careful monitoring should be used when co-prescribing CYP2C9 substrates with a narrow therapeutic index, such as phenytoin and warfarin.

Examples of these medications are listed in [Appendix 7](#), and these should be used cautiously with drug concentration monitoring where appropriate.

In addition to CYP3A, pamiparib can also be metabolized by CYP2C8 in human liver microsomes, but to a lesser extent. See [Appendix 7](#) for medications that should be used with caution for that reason.

7. STUDY PROCEDURES

7.1. Informed Consent

All patients will provide their written informed consent before the performance of any study related procedures.

A separate informed consent (Section 8.1) must be signed by patients who undergo collection of blood and/or biopsy to provide fresh tumor tissue sample for HRD/*BRCA* mutation central laboratory testing during prescreening.

During the informed consent process, male patients should be advised to seek advice on cryoconservation of sperm prior to treatment, because of the possibility of irreversible infertility due to therapy with temozolomide.

7.2. Patient Demographics and Other Baseline Characteristics

7.2.1. Demography

Demographic data will include gender, age or date of birth, race, and ethnicity.

7.2.2. Medical History

The medical history and prior medications assessments are the same for both the dose escalation and dose expansion phases of the study.

Clinically significant medical history findings (e.g., previous diagnoses, diseases, or surgeries) not pertaining to the study indication, which started before the patient signed the informed consent, and were considered relevant for the patient's study eligibility, will be collected and captured, including baseline severity, if ongoing, in the eCRF. Clinically significant is defined as any events, diagnoses, or laboratory values requiring treatment, follow-up, or the presence of signs or symptoms that require medical intervention. Concurrent medical signs and symptoms must be documented to establish baseline severities.

7.2.3. Cancer Characteristics

The following information will be collected: the date and stage of initial cancer diagnosis, anatomic site of metastases, all prior anticancer therapies including surgery, radiation therapy, and systemic treatments with dates administered. Start dates, stop dates, best response, and reasons for treatment discontinuation will be collected.

Patients with ovarian cancer are defined as platinum-sensitive if disease progression by RECIST v1.1 or GCIg CA-125 criteria had occurred more than 6 months after their last platinum chemotherapy. Ovarian cancer patients are defined as platinum-resistant if disease progression occurred less than 6 months after their last platinum chemotherapy but after their post-treatment evaluation, and as platinum-refractory if they experienced disease progression while receiving platinum chemotherapy, up to the date of their post-treatment evaluation.

7.2.4. Other Baseline Parameters

Information will also be collected regarding prior medications/significant non-drug therapies, smoking history, childbearing potential ([Appendix 2](#)) and any other assessments that are done for the purpose of eligibility for inclusion into the study (physical examination, vital signs, complete blood count [CBC] and blood chemistry, urinalysis, pregnancy test, and ECG). For further details on eligibility assessments, please see Section [5](#) and [Appendix 1](#).

7.3. Physical Examination, Vital Signs, ECOG Performance Status, Weight, and Height

A complete or limited physical examination, vital signs (systolic and diastolic blood pressure [SBP and DBP, respectively], pulse rate, oral, temporal, or tympanic temperature, and respiratory rate), weight, height (Screening only) and ECOG performance status will be performed at timepoints specified in [Appendix 1](#).

A complete physical examination should include an evaluation of general appearance as well as head, eyes, ears, nose and throat, neck, heart, chest (including lungs), abdomen, extremities, skin, lymph nodes, cardiovascular status and neurological status. A limited physical examination should be directed at the evaluation of symptoms or specific safety issues. New or worsening abnormalities should be recorded as AEs if appropriate.

ECOG performance status will be determined as outlined in [Appendix 8](#).

7.4. Adverse Events

Safety assessments should be performed at all site visits throughout the study. See [Appendix 1 Table 1](#) for the schedule of assessments and windows for assessments.

SAEs, regardless of the relationship to the study drug, will be collected from the time of patient informed consent. After initiation of study drug, all AEs and SAEs, regardless of relationship to study drug, will be reported until 30 days after the last study treatment or initiation of new anticancer therapy. All treatment-related AEs and SAEs will be followed until resolution or stabilization. The accepted regulatory definition of AEs and important additional requirements for SAE reporting are outlined in Section [10](#).

7.5. Electrocardiogram

During screening, a single 12-lead ECG with assessment of PR interval, QRS duration, and QTc interval will be obtained within 14 days of Cycle 1 Day1. The screening ECG will be read locally to determine eligibility.

Dose Escalation and Expansion Cohorts 1-5 ONLY

During Cycle 1 and the pamiparib PK intensive period (Day -2), ECGs will be performed in triplicate on a machine provided by the sponsor within a 5-minute window **prior** to pamiparib PK assessments (see below and Section [7.8](#)) at the timepoints indicated below:

- Pre-dose (within 30 min prior to dose)
- Post-dose:

- 1 hour (\pm 15 min)
- 2 hours (\pm 30 min)
- 4 hours (\pm 30 min)
- 6 hours (\pm 30 min)

ECGs for each patient should be obtained from the same machine whenever possible. Central read of ECGs obtained during the PK assessments will be performed for dose escalation and dose expansion cohorts 1-5.

Locally obtained ECGs should be performed if clinically indicated for all patients enrolled in the study. To minimize postural variability, it is important that patients are resting and in a supine position for \geq 5 minutes prior to each ECG collection. Blood draws and other procedures should be avoided during the period immediately before ECG measurement, and activity should be controlled as much as possible to minimize variability because of the effects of physiologic stress.

7.6. Laboratory Studies

Samples for a complete blood count (CBC), chemistry, and coagulation profiles will be drawn and analyzed locally. All other required blood samples will be sent to central laboratory for analysis throughout the study.

A detailed description of the procedures for sample collection, handling, storage, and shipment of the laboratory samples and all materials, such as test tubes and labels, is provided in the Study Manual.

Laboratory studies will be performed at the timepoints specified in [Appendix 1](#) (including allowed windows of assessment) and may also be performed as medically necessary. Laboratory assessments should be done before study drug administration.

Screening blood and urine tests must be performed within 14 days of Day 1. If they were performed within 4 days of Day 1, they do not need to be repeated on Cycle 1 Day 1.

7.6.1. Hematology Studies

A CBC includes hemoglobin, hematocrit, platelet count, red blood cell (RBC) count and white blood cell (WBC) count with differential.

7.6.2. Clinical Chemistry

Chemistry includes albumin, alkaline phosphatase (ALP), AST, ALT, bicarbonate, blood urea nitrogen (BUN), calcium, chloride, creatinine, glucose, lactic acid dehydrogenase (LDH), phosphate, potassium, sodium, total bilirubin, and total protein.

7.6.3. Coagulation

The coagulation profile includes international normalized ratio (INR) and activated partial thromboplastin time (aPTT), to be performed only at screening and as clinically indicated.

7.6.4. Hepatitis B and C Testing

Hepatitis B and C testing will be performed by a local laboratory at screening and as clinically indicated and will include HBV/hepatitis C virus (HCV) serology (hepatitis B surface antigen, hepatitis B surface antibody, hepatitis B core antibody, and HCV antibody) and viral load assessment (HBV DNA and HCV RNA).

7.6.5. Urinalysis with Dipstick

Urinalysis will be assessed using urine dipstick. Urine microscopy will be performed if urine dipstick is abnormal. Urinalysis includes pH, glucose, protein, ketones, bilirubin, blood, and specific gravity. If urine protein is $\geq 2+$ by dipstick, a 24-hour urine for total protein and a random urine for total protein and creatinine will be performed at screening only or as clinically indicated. All tests will be performed in local laboratories.

7.6.6. Pregnancy Test

Clinical Trial Facilitation Group (CTFG) recommendations related to contraception and pregnancy testing in clinical studies include for females with childbearing potential the use of highly effective forms of birth control ([Appendix 2](#)) and testing for pregnancy every 28 days. During screening, a serum pregnancy test must be obtained ≤ 7 days prior to Day 1. For subsequent pregnancy testing on study and at EOT, urine pregnancy tests are allowed. If a urine pregnancy test is positive, a confirmatory serum pregnancy test is required.

7.6.7. CA-125 Measurements

CA-125 levels will be collected for ovarian cancer patients and tested in a certified local laboratory during screening and every 8 weeks (± 7 days) following the first administration of the investigational medical product ([Appendix 1](#)).

Increases and decreases in CA-125 levels will be tracked in order to assess CA-125 responses by the GCIG criteria described in [Appendix 9](#).

7.6.8. PSA Measurements

PSA levels will be collected for prostate cancer patients and tested in a certified local laboratory during screening and every 8 weeks (± 7 days) following the first administration of the investigational medical product ([Appendix 1](#)). In addition, the three most recent PSA levels prior to screening will need to be provided to determine a baseline doubling time.

Increases and decreases in PSA will be tracked in order to assess PSA responses by the PCWG2 criteria described in [Appendix 10](#). PSA changes from baseline (either increment or decline) and maximal change in PSA will be recorded and responses assigned by PCWG2 criteria. PSA responses and progression must be confirmed 28 days later.

Although serial PSA will be measured in this study and PSA progression documented by the PCWG2 criteria, the PSA value on its own is not considered a reliable measure of clinical benefit and does not correlate tightly with survival. PSA flares may occur early in the study drug administration and may therefore confound response assessment. Additionally, there is emerging data that PARP-1 is implicated in multiple other essential cellular functions separate from DNA repair including ETS gene-mediated transcription regulation which may have a bearing on the

response assessments by PSA. PSA reading should not be applied as the sole criteria to consider discontinuation of study drugs. In absence of evidence of radiological or clinical evidence of disease progression, patients with mCRPC should continue in the study despite an increment in PSA. Therefore, patients will not be taken off study purely for rising PSA levels in the absence of worsening scans and symptoms since PARP inhibitors may impact tumor growth without impacting PSA secretion. PSA response and PSA progression will be defined according to the consensus guidelines of the PCWG2 criteria ([Appendix 10](#)).

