Anti-tumor activity will be evaluated by the treating investigator using standard RECIST v1.1 criteria (Appendix 5). Tumor response will also be evaluated according to the Gynecologic Cancer Intergroup (GCIg) criteria for patients with ovarian cancer. In addition, the Prostate Cancer Clinical Trials Working Group 2 (PCWG2) criteria will be used for patients with prostate cancer.

Patients who, at the time of progression, have an ongoing AE that leads to treatment discontinuation, will be followed until the event resolves, the investigator assesses the event as stable, the patient is lost to follow-up, or the patient starts a different anti-tumor therapy. If a patient discontinues study drug due to reasons other than disease progression or death, then tumor assessments should continue to be performed following the scheduled assessment plan until the start of new anticancer therapy, disease progression, death, lost to follow-up, or withdrawal of consent to efficacy follow-up.

In the absence of unacceptable toxicities or disease progression, patients will be offered continued study treatment of BGB-290 plus TMZ. Regardless of discontinuation of one or more study drugs, patients should continue on study with regular follow-up (Section 8.5). Patients who have discontinued all study drugs should return to the clinic for an end-of-treatment (EOT) visit within 7 days after the last study treatment (Section 8.4). After the EOT visit, patients should have regular follow-up for safety, efficacy, and survival as outlined in Section 8.5.

Study procedures and assessments are further detailed in Section 7 and Section 8, and a Schedule of Assessments can be found in [Appendix 1 Table 1](#).

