PSA	
On this study serial PSA measurements will be done every 8 weeks \pm 7 days after the first dose of Pamiparib in the first year and every 9 weeks \pm 7 days afterwards. Increases and decreases will be tracked in order to assess disease response. The PSA readings on its own will not be used to define progression in this protocol. PSA response and PSA progression will be defined according to the consensus guidelines of the PCWG 2:
 
 • PSA partial response is defined as a \geq 50% decline in PSA from Cycle 1 Day 1 (baseline) PSA value. This PSA decline much be confirmed to be sustained by a second PSA value obtained 4 or more weeks later. • PSA progression date is defined as the date that a \geq 25% increase and an absolute increase of \geq 2 ng/mL above the nadir is documented, which is confirmed by a second consecutive value obtained 4 or more weeks later. The first PSA reading will be obtained at week 12. 
Duration of PSA Response: Duration of PSA response is calculated from the time the PSA value first declines by at least 50% of the Cycle 1 Day 1 (baseline) value that has been confirmed by a second value until the time there is an increase of 25% of PSA nadir, provided the absolute increase is at least 2 ng/mL. The increase must be confirmed by a second consecutive measurement that is at least 25% above the nadir. If the PSA never shows a 25% increase over the nadir value, then the patient will be assessed at the last PSA measurement.

Target Lesions
	
Nodal or visceral progression sufficient for study entry independent of PSA measurable lesions not required for entry.
 
Use RECIST to record soft-tissue (nodal and visceral) lesions as target or non-target.
 
Only lymph nodes ≥ 2 cm in diameter should be used to assess for a change in size.
 
Record presence of nodal and/or visceral disease separately.
 
Progression at any scheduled reassessment ≥ 12 weeks does not need to be confirmed.

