6.3.4 CA-125 Assessment

For subjects with ovarian cancer, the CA-125 assessment result including elevated/normal and change from baseline (%) will be provided for each patient in a listing in SAF.

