6.3.5 PSA Assessment

For subjects with prostate cancer, PSA will be evaluated. The PSA assessment result including change from baseline and nadir (%) will be provided for each patient in a listing in SAF.

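### The protocol has PSA and CA-125 responses assigned under PCWG2 and GCIG criteria, but the SAP only lists the values; the gap matters mainly for bone-only patients in the prostate cohort

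*Protocol*

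**What the plan says.** **PSA in the protocol.** Section 7.6.8 has PSA measured at screening and every 8 weeks, and states that "maximal change in PSA will be recorded and responses assigned by PCWG2 criteria" and that "PSA responses and progression must be confirmed 28 days later". Appendix 10 defines a PSA partial response as a fall of 50% or more, measured as a "decline in PSA from Cycle 1 Day 1 (baseline) PSA value", and confirmed at least 4 weeks later. Section 4.1 says PCWG2 criteria will be used for prostate cancer. Section 11.2.5 reserves RECIST alone for tumors other than prostate cancer and has PSA and lesions judged together for prostate patients.

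**CA-125 in the protocol.** Section 7.6.7 says that changes in CA-125 "will be tracked in order to assess CA-125 responses by the GCIG criteria". Section 4.1 is firm: "Tumor response will also be evaluated according to the Gynecologic Cancer Intergroup" criteria in ovarian cancer. Section 11.2.5 is weaker and says only that GCIG criteria may be used. Appendix 9 gives the definition, the confirmation rule and the evaluable population.

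**The SAP.** Section 6.3.1 uses RECIST v1.1 by investigator for ORR, DCR, DOR and PFS in all cohorts. Section 6.3.5 says: "The PSA assessment result including change from baseline and nadir (%) will be provided for each patient in a listing in SAF". Section 6.3.4 says that "the CA-125 assessment result including elevated/normal and change from baseline (%) will be provided for each patient in a listing in SAF". Section 8 makes ORR, PFS and DOR radiographic and does not mention PSA, CA-125, PCWG2 or GCIG.

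**The concern.** The protocol collects two markers for a stated purpose, writes the response definitions and confirmation rules, and for prostate cancer puts the marker into the response determination itself. The SAP then creates no response variable from either marker, no combined PCWG2 or GCIG response, and no rate or interval. Section 8 of the SAP itemises smaller changes, such as moving vital signs and ECOG to listings, so its silence on the marker responses leaves a reader unable to tell a decision from an omission.

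At stake is how much Cohort 3 contributes to the antitumor-activity objective, which is primary. Criterion 14f admits men whose only disease is non-measurable bone lesions. The mCRPC studies described in Protocol 1.2 and 1.3 all report PSA in some form, and a listing gives no rate or interval to set beside them. If thresholds, confirmation rules and denominators are chosen after the data are seen in an open-label study, any marker rate reported later will carry less weight.

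**Working it through.** **1. Is there a planned marker response without an analysis?**

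| Item | Protocol | SAP |
|---|---|---|
| PSA response | Assigned by PCWG2, confirmed (7.6.8, Appendix 10) | Listing of percent change from baseline and nadir (6.3.5) |
| Prostate tumor response | PSA and lesions together (11.2.5) | RECIST only (6.3.1) |
| CA-125 / GCIG response | Will (4.1), may (11.2.5) | Listing of elevated/normal and percent change (6.3.4) |
| Declared change | – | ORR, PFS, DOR radiographic; markers not mentioned (8) |

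Yes for PSA. For CA-125 also yes, but on less firm text.

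**2. Who is affected?** In Appendix 5 a partial response is a fall of at least 30% in the sum of target-lesion diameters. A patient with only non-measurable lesions has no such sum, so PR is not available. A complete response remains possible, through disappearance of all non-target lesions with normal marker levels. Protocol 11.2.1 keeps criterion 14f prostate patients in the efficacy-evaluable population. SAP 6.1 requires measurable disease in the expansion phase and has no such exception. Read literally, bone-only patients leave the ORR table. Cohort 1 differs: criterion 11 requires measurable disease unless noted, and criterion 12 notes no exception, so RECIST ORR covers the ovarian patients.

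**3. Can the data support a confirmed rate?** PSA is scheduled every 8 weeks ± 7 days. The shortest gap between consecutive scheduled samples is 56 − 7 − 7 = 42 days, which exceeds the 28 days required.

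**4. What precision would a rate have?** Two-sided 90% Clopper-Pearson limits for x responders of n:

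- lower = 5th percentile of Beta(x, n − x + 1)
- upper = 95th percentile of Beta(x + 1, n − x)

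The plan's own ORR table (SAP Table 1, Protocol Table 5) comes first. 8/20 gives 21.7% to 60.6% (stated 22% to 61%) and 10/25 gives 23.6% to 58.3% (stated 24% to 58%). All 10 rows reproduce after rounding.

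The documents do not say how many patients will be marker-evaluable. Assuming 10 to 25, at an observed 40%:

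| Responders/evaluable | 90% CI | Half width (points) |
|---|---|---|
| 4/10 | 15.0% to 69.6% | 27.3 |
| 6/15 | 19.1% to 64.0% | 22.5 |
| 8/20 | 21.7% to 60.6% | 19.5 |
| 10/25 | 23.6% to 58.3% | 17.4 |

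At lower rates, 2/25 gives 1.4% to 23.1% and 5/25 gives 8.2% to 37.5%.

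**5. Who is CA-125-evaluable?** Appendix 9 needs a pretreatment value at least twice the upper limit and taken within 2 weeks before treatment. Appendix 1 schedules tumor antigens in the Day −28 to −1 screening window with no narrower limit, so a sample from Days −28 to −15 would not qualify. The evaluable number may therefore fall below the cohort size.

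**The case against.** The other side has real points.

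- **No named endpoint is lost.** Neither the protocol nor the SAP lists a PSA or CA-125 response rate as an endpoint. A reader might infer that a promised endpoint has been removed. The documents support less: a planned assessment was left without an analysis. A PSA-only table is also not the combined PCWG2 response of Protocol 11.2.5, so that response still needs its own statement.
- **The change is partly disclosed.** SAP Section 8 makes efficacy radiographic. That stands, but it names only ORR, PFS and DOR as examples and says nothing of the marker responses.
- **PSA is not the only measure for bone-only patients.** A reader might infer that it is. A non-target CR is possible, and SAP 6.3.2 summarises DCR and OS in the safety set, which includes these patients. Their expected number is not given.
- **The protocol discounts PSA.** Section 7.6.8 says PSA alone is not a reliable measure of clinical benefit and that flares may confound it. This is a reason to label a PSA rate supportive. The same section still calls for responses to be assigned.
- **Direct comparison is limited.** The cited veliparib plus TMZ study had a PSA fall of at least 30% as its primary endpoint. Its 2 of 25 (8%) confirmed responses are reported without a stated cut-off, so a 50% rate is not shown to be comparable. The olaparib study used a composite, and the abiraterone with or without veliparib study also reported measurable-disease response (80% versus 38%).
- **The ovarian case is weaker.** GCIG use is optional in 11.2.5, and RECIST covers Cohort 1.

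**Conclusion.** The point holds, chiefly for PSA in Cohort 3. The protocol commits to assigning PSA responses and to a PCWG2 determination. The SAP provides neither and does not declare the omission. Bone-only prostate patients are the ones for whom this costs information: they cannot have a PR, they drop out of the SAP efficacy set, and no estimate is made from their main response-type data. For CA-125 the inconsistency is genuine but of lower priority.

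A reader might also infer that a marker rate would be as precise as ORR. That is so only if all 20-25 patients are marker-evaluable. At an observed 40%, the 90% half width runs from about 17 points (10/25) to about 27 points (4/10). The range of 10 to 25 evaluable patients is an assumption, because the documents give no marker-evaluable share. RECIST ORR is unaffected as the primary response endpoint.

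**What to change.** 1. **SAP 6.3.5 (main change).** Add a supportive table for treated prostate patients with a pre-dose PSA: the evaluable count, and the number and percent with a PSA decline of at least 50% confirmed 4 or more weeks later (Appendix 10), with the exact 90% CI. Add a waterfall of best PSA change, so that other cut-offs such as 30% can be read from it. This denominator does not depend on measurable disease, so it keeps the bone-only patients.
2. **SAP 6.3.4 (lower priority).** Add the confirmed CA-125 response rate with exact 90% CI among patients evaluable under Appendix 9, applying both baseline conditions (at least twice the upper limit, and within 2 weeks before treatment), and show the evaluable count.
3. **SAP Section 8.** Keep RECIST ORR primary, and state which PCWG2 or GCIG combined responses will not be analysed and why.

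The cost is SAP wording, two small tables and one figure from data already collected. The downside is two more supportive results without multiplicity control, in a study with no hypothesis tests. The missing 14f exception in the SAP efficacy set needs its own reconciliation with Protocol 11.2.1, which these tables do not provide.
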